6.12.8. Patient Narratives

Patient narratives will be provided for all patients in the study who experience any of the following “notable” events prior to data cutoff for the submission:

- deaths
- SAEs
- discontinuations from study (or study drug) due to AEs
- pregnancy

A list of patients who meet the criteria for narratives will be provided.

6.13. CGM Analyses

The analyses described in this section will be based on the efficacy estimand, including data collected from first dose to last dose of study drug (i.e., open-label Humalog used during the lead-in period or IP used during the treatment period, excluding data (if any) that are collected while patients are temporarily off pump or off study treatment.

In addition, for the FDA submission, the analyses of the multiplicity adjusted objectives on CGM endpoints will also be performed for the ITT estimand. All of the variables will be derived for baseline, Visit 10 (Week 6-8), and Visit 13 (Week 14-16). For baseline, the variables will be derived based upon the data collected during the 2-week open-label Humalog treatment period. For Visit 10, the derivation will be based upon all the data collected during the visit interval of Visit 9, 10, and 11, taking into consideration that some patients may have the sensor inserted before Visit 9 or have the sensor removed after Visit 10.

[Table ITRO 6.5](#) lists all numerical measures for CGM data.

To ensure that the CGM outcome variables are only calculated from CGM session days with sufficient data within the 24-hour, daytime (0600 hours to midnight), or nighttime (midnight to 0600 hours) periods, the following criterion will be used to determine a valid CGM session day to be counted into the calculation for a visit: minimum number of measures per day – at least 70% of the total measures that are supposed to be obtained (i.e., 70% of the 288 measures) for the 24-hour period.

Similarly, for the by-meal outcome variables, the following criteria will be used to determine a valid CGM session day for a visit: minimum number of measures per day – at least 70% of the total measures that are supposed to be obtained. For example, 70% of the 24 measures for the iAUC_{0-2hr} after breakfast.

The definition and derivation of these variables are described in detail in [Appendix 2](#).

Table ITRO 6.5. Outcome Measures of CGM Data

Category	Endpoints	24-Hour	Daytime ^a	Nighttime ^b	By Meal ^c
Efficacy Endpoint: Glucose in the Target Ranges					
	Duration (in minutes) and percentage of time with sensor glucose values within target range 70 to 180 mg/dL [3.9 and 10.0 mmol/L], both inclusive	X	X	X	X
	Duration (in minutes) and percentage of time with sensor glucose values within target range 70 to 140 mg/dL [3.9 and 7.8 mmol/L], both inclusive	X	X	X	X
Efficacy Endpoint: Incremental AUCs (iAUCs) (after the start of meals)					
	iAUC _{0-1hr}				X
	iAUC _{0-2hr}				X
	iAUC _{0-3hr}				X
	iAUC _{0-4hr}				X
Efficacy Endpoint: Mean Glucose Excursions (after the start of meals) ^d					
	mean sensor glucose excursions 0 to 1 hour				X
	mean sensor glucose excursions 0 to 2 hour				X
	mean sensor glucose excursions 0 to 3 hour				X
	mean sensor glucose excursions 0 to 4 hour				X
Efficacy Endpoint: Hyperglycemic Episodes					
	Duration (in minutes) and percentage of time with glucose values >180, 181-250 and >250 mg/dL [10.0, 10.1-13.9 and 13.9 mmol/L] and hyperglycemic episodes, defined as at least 10 consecutive minutes >180, 181-250 and >250 mg/dL [10.0, 10.1-13.9 and 13.9 mmol/L]	X	X	X	
	Rate (events/patient/year) and incidence (percent of patients with at least 1 event) of hyperglycemic episodes, defined as at least 10 consecutive minutes >180, 181-250 and >250 mg/dL [10.0, 10.1-13.9 and 13.9 mmol/L]	X	X	X	
Efficacy Endpoint: Daily CGM Data Summary					
	Area under the curve (AUC)	X	X	X	
	Mean sensor glucose	X	X	X	
	Median sensor glucose	X	X	X	
	Hourly mean sensor glucose	X			

Category	Endpoints	24-Hour	Daytime ^a	Nighttime ^b	By Meal ^c
	Hourly median sensor glucose	X			
Efficacy Endpoint: Glucose Variability and Risk Assessment					
Within-Day	CV	X	X	X	X
	SD	X	X	X	X
	IQR	X	X	X	X
	MAGE	X	X		X
	LBGI: frequency and extent of low BG readings	X	X		X
	HBGI: frequency and extent of high BG readings	X	X		X
	BGRI = LBGI + HBGI: a measure of overall variability and risks of hypo- and hyperglycemia	X	X		X
Between-Day	CV	X	X	X	
	SD	X	X	X	
	MODD	X	X	X	
Overall ^e	CV	X	X	X	
	SD	X	X	X	
	IQR	X	X	X	
	LBGI	X	X	X	
	HBGI	X	X	X	
	BGRI	X	X	X	
Efficacy Endpoint: Premeal Glucose					
	Premeal Glucose				X
Efficacy Endpoint: Highest Postprandial Glucose					
	Time from start of meal to the highest postprandial glucose level (minutes) within 4 hours after meal(s)				X
	Highest postprandial glucose level within 4 hours after meal(s)				X
	Highest postprandial glucose excursion within 4 hours after meal(s)				X
Safety Endpoint: Hypoglycemic Episodes ^f					
	Duration (in minutes) and percentage of time with sensor glucose values <54, 54-69 and <70 mg/dL of hypoglycemic episodes, defined as at least 10 consecutive minutes <54, 54-69 and <70 mg/dL [3.0, 3.0-3.8 and 3.9 mmol/L]	X	X	X	X
	Rate (events/patient/year) and incidence (percent of patients with at least 1 event) of hypoglycemic episodes, defined as at least 10 consecutive minutes <54, 54-69 and <70 mg/dL [3.0, 3.0-3.8 and 3.9 mmol/L]	X	X	X	X

Category	Endpoints	24-Hour	Daytime ^a	Nighttime ^b	By Meal ^c
	Duration (in minutes) of hypoglycemic episode (defined as at least 10 consecutive minutes <54 mg/dL [3.0 mmol/L])		across all hypoglycemic episodes with duration at least 10 consecutive minutes		

Abbreviations: AUC = area under curve; BGRI = blood glucose risk index; CGM = continuous glucose monitoring; CV = coefficient of variation; HBGI = high blood glucose index; hr = hour; IQR = interquartile range; LBGI = low blood glucose index; MAGE = mean amplitude of glycemic excursions; MODD = mean of daily differences; SD = Standard deviation.

- a Daytime: 0600 hours to midnight (06:00:00-23:59:59 on the 24-hour clock).
- b Nighttime: midnight to 0600 hours (00:00:00-05:59:59 on the 24-hour clock).
- c By meals: for MMTT, and non-MMTT meals separately. Non-MMTT meals include all outpatient meals including morning (breakfast), midday (lunch) and evening (dinner) meals and overall (average across the 3 meals).
- d Mean sensor glucose measured at different time points (1, 2, 3 or 4 hours) after the start of the meal minus mean sensor glucose at the start of meal
- e Overall variability refers to the variability calculated based upon all the CGM measurements collected across all valid days for each derivation period.
- f In addition, postprandial hypoglycemia episodes during the following time interval after the start of each meal and overall will also be derived: <=1hr, <=2hr, >2 to <=4hr and <=4hr. The calculation will exclude any data collected after the next meal event.

To assess the glucose control over the course of approximately 3 days of continuous insulin infusion, the duration and percentage of time in ranges (target, hypoglycemia or hyperglycemia) and incremental AUCs after meals, will be derived based upon the CGM raw data collected on each of the infusion set wear days, including Day 1 (>0 and \leq 24 hours), Day 2 (>24 and \leq 48 hours), and Day 3 (>48 and \leq 72 hours) and summarized by treatment. In addition, only meals with the entire analysis interval (e.g., 0-1 hour after the start of the meal) on the same infusion set wear day will be included.

The meal time will be collected in the database by eCRF both for the MMTT and non-MMTT meals. The non-MMTT meals include all outpatient meals including morning (breakfast), midday (lunch) and evening (dinner) meals and overall (across the 3 meals). For the non-MMTT meals, only the first meal marker time will be used for each category (breakfast, lunch or dinner). Any data collected after the next meal (regardless of the category of the next meal) will be censored for the analysis with regards to the current meal. No outcome variables will be derived for bedtime meal but its time will be used to censor the data when deriving outcome variables for dinner. Time in ranges by meal will be derived for 0 to 1 hour, 0 to 2 hours, 0 to 3 hours and 0 to 4 hours after the start of each meal while variability by meal will only be derived for 0-4 hours.

All continuous variables will be analyzed using a similar MMRM model as used for the primary endpoint. If the percentage of patients with baseline missing (potentially due to missing meal event markers) is greater than 20% for any meal, a constrained longitudinal data analysis (cLDA) will be performed for all PPG-related CGM endpoints for that meal with treatment, strata (pooled country and patient's personal CGM use during the study), visit, and 2 dummy variables

to indicate treatment effect of LY90014 relative to Humalog at Visit 10 and Visit 13, respectively. An unstructured covariance structure will be used to model the within-patient errors. Significance tests will be based on LS means and Type III tests. SAS PROC MIXED will be used to perform the analysis. If this analysis fails to converge, the same order of the covariance structures will be tested as specified in Section 6.11.1.

Hypoglycemia/hyperglycemia rate per year as measured by CGM data will be analyzed using a negative binomial regression model with treatment as a covariate and an offset defined as the log transformation of days of CGM use/365.25 days. The proportion of patients with at least 1 hypoglycemia/hyperglycemia event as measured by CGM data (incidence) will be analyzed using a logistic regression model with treatment in the model. Similarly, proportion of patients who have achieved the guidance (Battelino 2019) recommended CGM targets of glycemic control (Table ITRO.6.6) during the 14 to 16 weeks of the treatment period will be summarized by treatment and analyzed using the same analysis methods.

Table ITRO.6.6. Guidance Recommended CGM Targets of Glycemic Control

Percentage of time with sensor glucose (24-hour)	Guidance Recommendation
target range	
70-180 mg/dL (3.9-10.0 mmol/L, both inclusive)	>70%
hypoglycemia range	
<70 mg/dL (3.9 mmol/L)	<4%
<54 mg/dL (3.0 mmol/L)	<1%
hyperglycemia range	
>180 mg/dL (10.0 mmol/L)	<25%
>250 mg/dL (13.9 mmol/L)	<5%

In addition, the following standardized glucose summary figures from the ambulatory glucose profile (AGP) will be generated, based upon the observed CGM data at baseline, Visit 10 and Visit 13:

- 24-hour period at individual patient level
- 24-hour period at the treatment level
- 0-4 hours relative to meal starting time at the treatment level, excluding data collected after the next meal event
- 0-4 hours relative to meal starting time by meal (breakfast, lunch and dinner) and by infusion set wear day (Day 1, Day 2, and Day 3) at the treatment level, excluding data collected after the next meal event

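### SAP 6.13 lists a treatment main effect in its constrained longitudinal model for by-meal CGM endpoints; fitted as written, the model leaves baseline unconstrained and loses precision

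*SAP*

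**What the plan says.** SAP 6.13 analyses continuous CGM variables by an MMRM like that of the primary endpoint, with a fallback: "If the percentage of patients with baseline missing (potentially due to missing meal event markers) is greater than 20% for any meal", then "a constrained longitudinal data analysis (cLDA) will be performed for all PPG-related CGM endpoints for that meal with treatment, strata". The strata are pooled country and personal CGM use. The list ends with "visit, and 2 dummy variables", whose purpose is "to indicate treatment effect of LY90014 relative to Humalog at Visit 10 and Visit 13, respectively" (the product code is misprinted in the source).

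The same section fixes the visits: "All of the variables will be derived for baseline, Visit 10 (Week 6-8), and Visit 13 (Week 14-16"). On estimation and testing it adds "An unstructured covariance structure will be used to model the within-patient errors" and "Significance tests will be based on LS means and Type III tests". It names no contrast. It does not say that the treatment term is set to zero at baseline or that the arms share a baseline mean.

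The other mentions of a cLDA concern the MMTT serum PPG (protocol 10.3.3.2; SAP 6.11.2 and the footnote to Table ITRO 6.2). They list no model terms, so they do not settle the question.

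**The concern.** A constrained longitudinal model treats baseline as one of the outcomes and gives the randomised arms one common baseline mean. It therefore has visit terms and post-baseline treatment terms, but no treatment main effect. Adding that main effect to the two dummies frees the baseline difference between arms, a difference that arises before randomised treatment starts and is zero in expectation. The sentence then disagrees with itself: the model is called constrained but is not, and the dummies are described as effects at a visit but estimate something else.

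At stake are the standard errors, and the meaning of the reported coefficient, for every PPG-related CGM endpoint of a meal that meets the trigger. There is also a labelling hazard. If the dummies are coded 0/1 as covariates, the Type III test printed for treatment in the listed model is a test of the baseline difference, and the SAP does not say which test is to be reported.

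**Working it through.** The plan states no figure for this model, so there is none to reproduce.

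**1. What the listed terms fit.** Let T = 1 for LY900014, and let V10 and V13 indicate the visits. Leaving out the strata, which shift all cells alike, the listed mean is

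α + β10·V10 + β13·V13 + τ·T + δ10·T·V10 + δ13·T·V13.

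| Arm difference (LY900014 − Humalog) | Terms as listed | Without treatment |
|---|---|---|
| Baseline | τ | 0 |
| Visit 10 | τ + δ10 | δ10 |
| Visit 13 | τ + δ13 | δ13 |

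There are 2 × 3 = 6 cell means. The listed design has rank 6, so it is saturated. Without the treatment term the rank is 5, and the one restriction is the shared baseline mean. As listed, δ13 = (Visit 13 difference) − (baseline difference), a difference in change. Only without the treatment term is it the effect at Visit 13.

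**2. Precision.** The assumptions, none of them from the documents, are: equal variance σ² at each visit; common correlation ρ between visits; baseline missing at random in the same fraction m of each arm; Visits 10 and 13 observed; n per arm. Variances are in units of 2σ²/n, so n cancels from the ratios.

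- Share of baseline variance not explained by Visits 10 and 13: R = 1 − 2ρ²/(1+ρ).
- Variance of the estimated baseline difference in the listed model: k = R/(1−m) + (1−R).
- True cLDA, Visit 13 effect: 1 − ρ²/k.
- Listed model, Visit 13 dummy: 1 + k − 2ρ.
- Listed model, Visit 13 LS-mean difference: 1.
- MMRM with baseline as covariate, dropping patients without a baseline: (1−ρ²)/(1−m).

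Example with ρ = 0.5 and m = 0.2:
- R = 1 − 0.5/1.5 = 0.6667, and k = 0.6667/0.8 + 0.3333 = 1.1667.
- cLDA = 1 − 0.25/1.1667 = 0.7857.
- Dummy = 1 + 1.1667 − 1 = 1.1667; ratio 1.1667/0.7857 = 1.485.
- LS-mean difference: ratio 1/0.7857 = 1.273.
- MMRM = 0.75/0.8 = 0.9375; ratio 0.9375/0.7857 = 1.193.

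Variance relative to a true cLDA (a full generalised-least-squares calculation gives the same values):

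| m | ρ | Visit 13 dummy | Visit 13 LS-mean difference | MMRM, no-baseline patients dropped |
|---|---|---|---|---|
| 20% | 0.3 | 1.745 | 1.080 | 1.228 |
| 20% | 0.5 | 1.485 | 1.273 | 1.193 |
| 20% | 0.7 | 1.267 | 1.796 | 1.145 |
| 20% | 0.8 | 1.171 | 2.481 | 1.116 |
| 40% | 0.3 | 2.094 | 1.061 | 1.609 |
| 40% | 0.5 | 1.747 | 1.209 | 1.512 |
| 40% | 0.7 | 1.428 | 1.618 | 1.376 |
| 40% | 0.8 | 1.279 | 2.158 | 1.295 |

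Taking square roots, the standard error is 1.08 to 1.45 times that of a true cLDA for the dummy, and 1.03 to 1.58 times for the LS-mean difference. At 20% missing, the dummy is less precise than an MMRM that drops patients without a baseline at every correlation examined. At 40% missing and ρ = 0.8 the order reverses slightly (1.279 against 1.295).

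**The case against.** The strongest reply is that this is loose wording. The SAP names the method, provides dummies only for the two post-baseline visits, and describes them as treatment effects at those visits. All of that is the cLDA parameterisation, and treatment may simply be listed as a factor in play. This stands in part: a true cLDA may well be what was meant and what would be programmed. A reader might infer that the analysis will certainly leave baseline unconstrained, and the documents do not support that. They do show a term list that conflicts with the named method, with nothing elsewhere to resolve it.

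Second, a reader might infer that the fallback defeats a stated precision aim. SAP 6.13 gives only one reason for switching, missing baselines, and the listed model does keep those patients. A precision motive can only be inferred: a methods paper on cLDA efficiency is cited, but for the MMTT analysis.

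Third, the size depends on a contrast the SAP does not name. The complete-data ratio for the dummy, 2/(1+ρ), is tempting but describes a case that cannot arise, because the model is used only above 20% missing. Nor does the loss always grow with missingness. It does for the dummy, but for the LS-mean difference at ρ = 0.5 it falls from 1.273 at 20% missing to 1.209 at 40%. This objection stands, which is why both contrasts are shown as ranges.

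**Conclusion.** The inconsistency is real. Fitted as written, the model is saturated, the arms have separate baseline means, and the dummies do not carry the meaning the SAP gives them. Under the assumptions above, the variance relative to a true cLDA is 1.17 to 2.09 times for the Visit 13 dummy, or 1.06 to 2.48 times for the Visit 13 LS-mean difference. Those ranges rest on assumed correlations and missing rates. The loss of precision for either contrast does not depend on the exact values chosen.

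A reader might also infer bias, or damage to the key results. Neither follows. Both contrasts are unbiased under randomisation and missing at random. The model is a conditional, meal-by-meal fallback for PPG-related CGM endpoints. By-meal incremental AUC is a tertiary objective (SAP Table ITRO 4.1, objective 27), CGM outcomes outside the secondary set are exploratory (SAP 6.11.5), and neither has multiplicity adjustment (SAP 6.5). HbA1c, the MMTT serum PPG and time in range over 24 hours and daytime are not affected. The point calls for a clarification of modest consequence.

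**What to change.** In SAP 6.13, remove treatment from the cLDA term list, or state that baseline means are constrained equal across arms. Keep strata, visit (baseline, 10 and 13), the two post-baseline dummies and the unstructured covariance. Name the Visit 13 dummy coefficient as the tested contrast, in place of the unspecified LS-means and Type III tests. Removing the term alone is not enough: without a treatment class effect there is no treatment LS-mean comparison to test, and the arm means at each visit have to be built from the visit and dummy coefficients.

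The cost is a sentence or two in the SAP and the matching programming specification. No new data or design change is needed. If the SAP is no longer open to revision, SAP 6.1 allows a change of this kind to be described and justified in the clinical study report.

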6.2. Adjustments for Covariates

Stratification factors of this study include country, HbA1c stratum ($\leq 7.5\%$, $> 7.5\%$), and patient's personal CGM or FGM use during the study. Stratification factors will be entered into the IWRS for randomization and also collected in the database by electronic case report form (eCRF) or central laboratory. The analysis models will use the stratification factors as collected at randomization in the database as fixed effects.

For the primary analysis of HbA1c, the stratification factor of HbA1c stratum will not be included. Instead, the continuous value of baseline (Visit 4) HbA1c will be included in the analysis models.

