- actual and change from baseline in fasting glucose (average of measurements at time -15 and 0), and PPG at 15, 30, 60, 120, 180, and 240 minutes after the meal
- PPG excursions at time 15, 30, 180, and 240 minutes after the meal (PPG minus fasting glucose)

Sensitivity analysis for PPG and excursions may be performed to exclude patients whose PPG and excursion could be affected by factors including MMTT consumption amount (for example, partial MMTT was consumed).

Treatment comparisons for the proportion of patients with HbA1c $< 7.0\%$ and $\leq 6.5\%$ will be analyzed using a longitudinal logistic regression with repeated measurements conducted by a generalized linear mixed model including independent variables of treatment, baseline HbA1c value, visit, baseline HbA1c-by-visit interaction, and treatment-by-visit interaction. An unstructured covariance structure will be used.

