Within-day and between-day glycemic variability measured by the SD and the coefficient of variation (CV) of 10-point SMBG profiles will also be analyzed by the MMRM model specified in Section 6.11.4. At a given visit, the CV and SD on each day with a valid SMBG profile will be calculated using all the glucose values within that day, then the average values of these CVs and SDs will be used as the within-day CV and SD at that visit in analysis. At a given visit, the CV and SD at each of the 10 pre-specified SMBG time points will be calculated using the corresponding glucose values of the valid SMBG profiles, then the average values of these CVs and SDs will be used as the between-day CV and SD at that visit in analysis.

The 1-hour and 2-hour PPG excursions by 10-point SMBG profile and daily average of the 10-point SMBG profile will be analyzed similarly.

The following additional variables from the MMTT will be analyzed using the ANCOVA model described in Section 6.11.2:

- Incremental areas under the serum glucose concentration-time curve (iAUC) from 0 to 30 minutes, 0 to 1 hour, 0 to 2 hours, 0 to 3 hours, and 0 to 4 hours after the meal in MMTT. iAUC is the total area under the serum glucose curve but above the glucose level at time 0 (average of measurements at time -15 and 0) when the meal starts for the MMTT within the specific time frame. The area will be calculated by trapezoids rule.
- Area under/above the serum glucose concentration time curve from 0 to 30 minutes, 0 to 1 hour, 0 to 2 hours, 0 to 3 hours, and 0 to 4 hours after the meal in MMTT.
 - AUC: Total area under the serum glucose curve calculated by trapezoids area within the specific time frame
 - AUC>180: Total area under the serum glucose curve but above the 180 mg/dL level within the specific time frame
 - AUC≤70: Total area above the serum glucose curve but below the 70 mg/dL level within the specific time frame.
- Glucose variability during MMTT (CV and SD of all serum glucose values collected during the MMTT).

The incidence of patients with HbA1c <7.0% and ≤6.5% at Week 16 (Visit 13), imputed using LOCF, and no severe hypoglycemia during 16 weeks of treatment will be compared using a logistic regression model with terms for treatment and baseline HbA1c value.

In addition, CGM outcomes that are not included in the secondary efficacy endpoints will be analyzed as exploratory efficacy endpoints. Details for the CGM analyses can be found in Section 6.13.

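### SAP 6.13 tests attainment of the CGM targets with a treatment-only logistic model, leaving out the lead-in value of the same CGM percentage: a valid test, but less efficient than it could be

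*SAP*

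**What the plan says.** Table ITRO.6.6 in SAP 6.13 lists five 24-hour targets: more than 70% of time in 70-180 mg/dL, less than 4% below 70, less than 1% below 54, less than 25% above 180 and less than 5% above 250 mg/dL. Attainment of these "recommended CGM targets of glycemic control (Table ITRO.6.6) during the 14 to 16 weeks of the treatment period will be summarized by treatment and analyzed" by the methods of the preceding sentences. For a proportion, the method named there is that it "will be analyzed using a logistic regression model with treatment in the model". No baseline value and no stratum is mentioned.

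The baseline measurement exists. SAP 6.13 states: "For baseline, the variables will be derived based upon the data collected during the 2-week open-label Humalog treatment period". The same section analyses the continuous CGM variables with an MMRM similar to the primary model, which SAP 6.11.1 specifies with the baseline value and strata.

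The HbA1c responder analyses do use baseline. SAP 6.11.4 specifies a "generalized linear mixed model including independent variables of treatment, baseline HbA1c value, visit, baseline HbA1c-by-visit interaction, and treatment-by-visit interaction", and SAP 6.11.5 a "logistic regression model with terms for treatment and baseline HbA1c value" for the target-without-severe-hypoglycemia composite.

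On strata, SAP 6.2 says in general terms: "The analysis models will use the stratification factors as collected at randomization in the database as fixed effects".

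**The concern.** Whether a patient ends above 70% time in range is likely to depend heavily on where that patient started. The lead-in percentage comes from the same blinded sensor over a planned 14 days, so it is a natural covariate that needs no new data. Leaving it out of a logistic model for a dichotomised outcome lowers the chance of detecting a true effect and leaves chance baseline imbalance uncorrected.

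The SAP gives no reason for the difference in handling. The same percentages are baseline-adjusted when analysed as continuous variables but not once they are cut at a threshold, and HbA1c thresholds are adjusted where CGM thresholds are not. The treatment-only model is the one used for hypoglycemia event incidence, and it appears to have been extended to a measure that has a direct baseline counterpart.

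**Working it through.** **Plan's own figures.** The documents state no power for target attainment. The sample size section (protocol 10.1, SAP 5.2) supplies only the number per arm. With 184 completers per arm and SD 0.88, the standard error is 0.88 × √(2/184) = 0.0917.
- Margin 0.4: 0.4/0.0917 − 1.96 = 2.40, power 99.2% (stated: at least 99%).
- Margin 0.3: 0.3/0.0917 − 1.96 = 1.31, power 90.5% (stated: 90%).
- 368/0.88 = 418.2, so 419 randomized (stated: about 420).

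These figures reproduce. The 184 is an HbA1c completer count and is borrowed here for CGM.

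**Assumptions, none from the documents.** Baseline and Week 14-16 time in range are bivariate normal with mean 58%, SD 12 points and correlation r. The true gain on LY900014 is 4 points. The test is a two-sided 0.05 Wald test of treatment.

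**Attainment of >70%.**
- Humalog: 1 − Φ((70 − 58)/12) = 1 − Φ(1.00) = 15.9%.
- LY900014: 1 − Φ((70 − 62)/12) = 1 − Φ(0.667) = 25.2%.

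**Treatment-only power by formula.** The standard error is √[(0.159 × 0.841 + 0.252 × 0.748)/184] = 0.0418. Then z = 0.0938/0.0418 = 2.24, and power = Φ(2.24 − 1.96) = 61%. This power does not depend on r. Simulation gave 59 to 62%.

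**Power with baseline added** (4,000 simulated trials per cell, Monte Carlo error about 0.8 point; missing baselines are missing at random):

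| r | Treatment only | Adjusted, baseline complete | 10% missing: complete-case / mean-imputed | 15% missing: complete-case / mean-imputed |
|---|---|---|---|---|
| 0.4 | about 60% | 63% | 60% / 63% | 58% / 64% |
| 0.5 | about 60% | 66% | 62% / 66% | 60% / 67% |
| 0.7 | about 60% | 75% | 71% / 72% | 69% / 73% |
| 0.8 | about 60% | 82% | 77% / 79% | 76% / 78% |

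A separate run of the complete-baseline case put adjusted power at about 65%, 67%, 75% and 82%, which agrees apart from simulation noise at low r. The gains are therefore about 3 to 5 points at r = 0.4, 5 to 7 at 0.5, 14 to 15 at 0.7 and 21 to 23 at 0.8.

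With no true effect (15,000 trials per cell, r = 0.5 and 0.8, 0 and 15% missing), rejection was 4.4 to 5.4% in every model.

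**Sensitivity to effect size.** With control attainment set at 35% instead and r from 0.5 to 0.8, the gain was about 2 to 6 points when treatment-only power was near 11% and about 2 to 3 points when it was near 97%. It was largest in the middle, for example 62% to 87% at r = 0.8.

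**Strata.** Adding three simulated strata on top of baseline changed power by no more than 0.6 point.

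**The case against.** The strongest reply is that little rests on this analysis. Target attainment is not among H1 to H6, is not listed as an endpoint in SAP Table ITRO 4.1, and has no multiplicity adjustment under SAP 6.5. Time in range over 24 hours and over daytime is tested inside the graphical procedure as a continuous, baseline-adjusted measure. An effect on glucose ranges would be looked for there first. The treatment-only model also gives a marginal odds ratio that matches the displayed proportions and uses every patient with Week 14-16 data. All of this stands, and it keeps the point minor.

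The second reply is that adjustment is not free. A model that drops patients without a valid lead-in session gains almost nothing at r = 0.5, and loses about 2 points at r = 0.4 with 15% missing. This also stands. It rules out a complete-case version but not adjustment itself, since mean imputation keeps everyone and restores the gain.

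A reader might infer that SAP 6.13 contradicts SAP 6.2 by leaving out the strata. The documents do not support that firmly. SAP 6.2 is a general statement, and the HbA1c responder models and the hypoglycemia models name no strata either. If SAP 6.2 is binding, the strata are already included. The text leaves open which reading governs; it does not show a breach.

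**Conclusion.** The point holds as a matter of efficiency and consistency. The SAP leaves out a prognostic value that it already derives, and handles CGM targets differently from HbA1c targets without giving a reason.

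Under the stated assumptions the cost for the >70% target runs from about 3 points of power at r = 0.4 to about 20 or slightly more at r = 0.8. A reader might infer one fixed loss for the whole table. The documents do not support that, because they give no mean, SD, correlation or effect for time in range. Only one of five targets was computed. The low-percentage targets (below 54, below 70 and above 250 mg/dL) are bounded at zero, and the normal model used here may fit them poorly.

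Nor does the omission make the test invalid: type I error stays near 5%, and no confirmatory claim depends on the result.

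**What to change.** In SAP 6.13, specify the target-attainment logistic models with treatment and the baseline (lead-in) percentage for the same glucose range. Where baseline CGM is missing, impute the overall baseline mean across both arms so that no patient is dropped. Report the observed proportions and a standardised risk difference, and keep the treatment-only model as a sensitivity analysis or as the fallback if the adjusted model does not converge. State whether the SAP 6.2 strata apply to this model; the reason to settle it is clarity, since they add almost no power once baseline is in.

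The cost is a sentence or two in the SAP, fixed before unblinding. No new data and no change to the alpha allocation are needed. Protocol 10.3.3.3 leaves tertiary analysis details to the SAP, so a protocol amendment should not be needed. The downside is that the odds ratio becomes conditional on baseline, which is why the proportions and the risk difference are reported beside it.
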